5.3 Semi-Structured Qualitative Interview

A semi-structured, qualitative interview guide designed by the study team for use with AYA and caregiver(s) (assigned to DECIDES or DECIDES + coach), and oncology health care providers. The purpose of the interview is to obtain further information from participants about the process of treatment decision-making and their experience using DECIDES, the decision aid. Participants will be interviewed by a study team member via remote video conference software (Microsoft Teams). All interviews will be audio and/or video recorded and professionally transcribed (by a CHOP-approved vendor with a BAA in place), and the interview data will be analyzed.

Table 1. Measures

Construct	Measure	Administration	
		T1	T2
Demographics	Electronic Health Record; AYA/Caregiver Self-Report	AYA, CG	
Treatment Intensity	Intensity of Treatment Rating Scale (ITR-3) ⁽⁹⁹⁾	PR	
Acceptability ^(D)	Acceptability of the Decision Aid ⁽⁶⁾		AYA, CG
Usability ^(D)	The Systems Usability Scale ^(36,71)		AYA, CG, PR
AYA Involvement in Shared Decision-Making	Control Preferences ^(74,75)		AYA, CG
	Physician Decision-Making Scale ⁽¹⁰⁰⁾		AYA, CG
	Shared-Decision Making Questionnaire (SDM-Q-9) ⁽⁹⁴⁾		AYA, CG
Knowledge	AYA Hope Survey: Information Need ^(76,77)	AYA, CG	
	Knowledge of Clinical Trials ⁽⁶⁴⁾	AYA, CG	AYA, CG
Attitudes to Clinical Trials	Pediatric Research Participation Questionnaire	AYA, CG	AYA, CG
Alignment of Decision with Values	(PRPQ) ^(15,16)		AYA, CG
Decision-Making	Certainty	Decisional Conflict Scale ⁽⁶⁵⁾	AYA, CG
	Satisfaction	Satisfaction with Decision Scale ⁽⁶⁶⁾	AYA, CG
	Self-Efficacy	Decision Self-Efficacy Scale ⁽⁶⁷⁾	AYA, CG
	Regret	Decision Regret Scale ⁽⁷²⁾	AYA, CG
Health-Related Quality of Life	PROMIS Parent Proxy Profile-25 ⁽⁹⁸⁾	CG	CG
	PROMIS Pediatric Profile-25 ⁽⁹⁷⁾	AYA (15-17)	AYA (15-17)
	PROMIS-29 Profile ⁽⁹⁶⁾	AYA(18-24)	AYA(18-24)
*Distress	Distress Thermometer ⁽⁷³⁾	AYA, CG	AYA, CG
*Valence and Arousal	Affective Slider ⁽⁸⁷⁾	AYA, CG	
*Awareness of Feeling Emotions	Affective Orientation (AO15) ⁽⁸⁸⁾	AYA, CG	
*Developmental Status	Developmental Task Questionnaire ^(89,92)	AYA	
*Psychosocial Maturity	Consideration of Future Consequences ⁽⁹⁰⁾	AYA, CG	
	Psychosocial Maturity Inventory ⁽⁹⁵⁾	AYA	
	Emotion Regulation Questionnaire ⁽⁹¹⁾	AYA, CG	
*Problem-Solving	Family Assessment Device (FAD): Problem-Solving ⁽⁹³⁾	AYA, CG	
Semi-Structured Qualitative Interview ^(D)	DECIDES Interview Guide		AYA, CG, PR

* = Covariate

(D) = measure for participants randomized to DECIDES or DECIDES + coach only

T1 = Pre-Intervention; T2 = Post-Intervention; AYA = Adolescent/Young Adult; CG = Caregiver; PR = Health Care Provider

6 STATISTICAL CONSIDERATIONS

Demographic characteristics and all measurements will be summarized.

6.1 Primary Endpoints

Hyp 1a. We will perform descriptive analyses of responses to the acceptability questionnaire. Click behavior, participation rate, and time to DECIDES implementation will be summarized to describe feasibility.

Hyp 1b. We will use qualitative descriptive methods ⁽⁶¹⁾ to evaluate acceptability, usability, and feasibility. Interviews with AYA, caregiver(s) and oncology health care providers will be audio and/or video-recorded and transcribed. Constant comparative methods (using Atlas.ti) will be used to simultaneously gather and rigorously analyze data using two coders to ensure coding reliability.

Hyp 1c. Feasibility measures such as participation rate and summary score for the Systems Usability Scale will be summarized for DECIDES alone and DECIDES + coach separately, along with 95% confidence intervals (CIs). We expect that participation rate and usability score will be higher for the DECIDES + coach group.

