2 STUDY OBJECTIVES

2.1 Primary Objective (or Aim)

The primary objective of this study is to assess the acceptability and feasibility of DECIDES using mixed methods and use results to inform implementation strategies for future dissemination.

Hyp 1a. Based on AYA, caregiver(s), and oncology health care provider ratings, and usage analytics, DECIDES will be acceptable and feasible during treatment decision-making within 6 weeks of diagnosis.

Hyp 1b. Qualitative interviews with AYA and caregiver(s) (randomized to DECIDES and DECIDES + coach) and oncology health care providers will confirm acceptability and feasibility ratings and provide specific information regarding timing, utility, barriers/facilitators, ease of use, and modifications to DECIDES for future implementation.

Hyp 1c (exploratory). DECIDES + coach will be rated more usable than DECIDES alone.

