3 INVESTIGATIONAL PLAN

3.1 General Schema of Study Design

This is a 3-arm, mixed methods, hybrid design trial. We expect to enroll up to 65 family units to produce at least 50 evaluable family units that are randomized to participate in one of the following intervention groups:

- Usual Care (n=10)
- DECIDES (n=20)
- DECIDES + coach (n=20)

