6.2 Secondary Endpoints

The secondary objective is to evaluate preliminary efficacy of DECIDES using a randomized trial.

Hyp 2a and Hyp 2b. Because all measures are continuous, the primary analyses will be summarizing mean and 95% CI by groups and two-sample t test comparing groups for the post-intervention outcome measures. With the sample size of 20 family units for each DECIDES group and 10 family units for usual care, we will have 80% power to detect an effect size of 1.26 (that is, mean difference between the two groups is 1.26 x Standard Deviation).

Hyp 2c. Each AYA and caregiver will have two value scores: Σ factors endorsed as supporting enrollment/ Σ factors endorsed as not supporting enrollment. Consistency of value to enrollment decision will be evaluated with Tetrachoric correlation with 95% CI.

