8 STUDY ADMINISTRATION

8.1 Treatment Assignment Methods

8.1.1 Randomization

We will enroll up to 65 family units to achieve 50 evaluable family units that are randomized to three groups with a 1:2:2 ratio for usual care, DECIDES, and DECIDES +

coach. The randomization will be stratified by two age categories, under 18 years old and 18 years or older, and we expect 50% of the AYA patients in each of the two strata. For each stratum, we use a blocked randomization of block size of 5. The statistician will generate the randomization sheet for assigning patients into intervention groups.

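### Hyp 1c compares DECIDES + coach with DECIDES alone, but section 6.1 plans no estimate of the difference between the two arms

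*Combined protocol and SAP*

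**What the plan says.** Section 2.1 states the hypothesis as a comparison and marks its status: "Hyp 1c (exploratory). DECIDES + coach will be rated more usable than DECIDES alone". Section 6.1 gives the analysis. Participation rate and the SUS summary score "will be summarized for DECIDES alone and DECIDES + coach separately, along with 95% confidence intervals (CIs". It then adds a direction: "We expect that participation rate and usability score will be higher for the DECIDES + coach group". It names no between-arm difference, no interval for a difference, no test and no decision rule.

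The only between-group analysis in the plan is the two-sample t test in section 6.2. It stands under Hyp 2a and 2b, which section 2.2 defines as contrasts with Usual Care on involvement, shared decision-making and decision processes. Usability and participation rate are not among those outcomes.

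**The concern.** Hyp 1c concerns one quantity, coach minus no coach, and the planned output is two one-arm summaries. It is also the only hypothesis that sets the two DECIDES arms against each other, and those arms hold 40 of the 50 evaluable family units. The primary objective is to use results to shape implementation, and the value of adding a coach is a natural question there.

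Two intervals printed side by side invite the reader to check whether they overlap. That check is much stricter than asking whether an interval for the difference excludes zero. A real difference could be read as none.

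**Working it through.** **The plan's own figure.** None is given for Hyp 1c. The only power statement is in section 6.2: 80% at 1.26 SD for 20 v 10, under Hyp 2a and 2b. No alpha is stated. By the noncentral t, power there is 88.1% at two-sided 0.05 and 80.6% at two-sided 0.025. It concerns contrasts with Usual Care and does not bear on Hyp 1c.

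**Inputs for Hyp 1c.**
- Arm size is 20 v 20 evaluable family units (section 6.2: "With the sample size of 20 family units for each DECIDES group and 10 family units for usual care"). The section 8.1.1 allocation, "randomized to three groups with a 1:2:2 ratio for usual care", makes these two arms 1:1.
- The level is 95%, from section 6.1, taken as two-sided 0.05 (assumption).
- SUS runs from 0 to 100 (section 5.2). No SD or expected gap is given, so gaps are in SD units.
- One score per family unit, equal SDs and normal data (assumptions).

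**Step 1: interval widths.**
- Half-width of each arm's own CI: t(0.975, 19)/√20 = 2.093/4.472 = 0.468 SD.
- The two intervals separate only if the observed gap exceeds 2 × 0.468 = 0.936 SD.
- Half-width of a CI for the difference: t(0.975, 38) × √(1/20 + 1/20) = 2.024 × 0.3162 = 0.640 SD.

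With equal observed SDs, any observed gap between about 0.64 and 0.94 SD gives overlapping arm intervals together with a difference interval that excludes zero.

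**Step 2: what an overlap reading would cost.** Power of the direct comparison is from the noncentral t. Power of non-overlap is from 400,000 simulated trials per gap.

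| Assumed true gap (SD) | Difference CI excludes zero | Arm CIs do not overlap | Share of power lost |
|---|---|---|---|
| 0 | 5.0% | 0.56% | – |
| 0.3 | 15% | 3% | 80% |
| 0.5 | 34% | 10% | 70% |
| 0.8 | 69% | 36% | 49% |
| 0.909 | 80% | 48% | 40% |
| 1.0 | 87% | 59% | 32% |
| 1.26 | 97% | 84% | 13% |

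Normal check: Φ(d/√(2/20) − 1.96√2). At d = 0.886, where the normal approximation gives the direct comparison 80% power, this is Φ(2.802 − 2.772) = 51%.

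**Step 3: participation rate.** With assumed true rates, 20 per arm, and Wilson intervals per arm against a Newcombe interval for the difference: 0.5 v 0.9 gives 50% by non-overlap and 84% by the difference interval; 0.6 v 0.9 gives 25% and 62%.

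**Step 4: can the SUS difference be recovered from the planned output?** Each arm's standard error is 0.468/2.093 = 0.2236 SD. The standard error of the difference is √(0.2236² + 0.2236²) = 0.316 SD, which returns ±0.640 SD. So an unadjusted SUS difference and its interval can be derived. They would not be pre-specified and would not reflect the age stratification of section 8.1.1.

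**The case against.** The strongest reply is that description suits the status of the hypothesis. Hyp 1c is the only one marked exploratory, section 6.1 is descriptive or qualitative throughout, and formal testing is kept for Hyp 2a and 2b. With 20 per arm and no SUS effect size, estimating each arm is a reasonable pilot choice. This stands as an argument against requiring a test. It does not remove the case for an estimate, because an exploratory comparison still needs its difference and its uncertainty.

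Some stronger readings are tempting, and the documents do not support them:
- *That Hyp 1c will be judged by overlapping intervals.* No section says so. The power loss belongs to a possible misreading, not to a planned test.
- *That the trial could not state the size or precision of the difference.* Step 4 shows that an unadjusted SUS difference follows from the two arm summaries.
- *That a fixed share of power, such as a third, is lost.* The share runs from 80% to 13% as the assumed gap goes from 0.3 to 1.26 SD, and the documents give nothing to choose among these.
- *That this figure decides whether a coach is carried into later work.* Section 2.1 says only that results will inform implementation strategies. There is no go/no-go rule on SUS.

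The 20 v 20 figures also do not carry over directly to caregivers. Section 3.2.2 allows AYA aged 18 or older to take part alone and allows triads, so caregiver numbers may differ from 20 and scores may be correlated within a family.

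**Conclusion.** The point holds as a minor one. A hypothesis about a difference between two randomized arms has no planned estimate of that difference, and nothing elsewhere in the plan supplies it. This does not depend on any power figure. Under the stated assumptions, an interval for the SUS difference would be about ±0.64 SD. If readers relied on overlap instead, power at an assumed true gap of 0.91 SD would be about 48% rather than 80%. These sizes are illustrative, since the documents give neither a SUS SD nor an expected gap.

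**What to change.** Add to Hyp 1c in section 6.1:
- the mean SUS difference, DECIDES + coach minus DECIDES, with its 95% CI, adjusted for the randomization age stratum, for AYA and for caregivers separately. The caregiver analysis should allow for two caregivers in one family, for example with a random family effect;
- the difference in participation proportions with a 95% CI, for example Newcombe's.

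Present both as exploratory estimates without a test, and keep the per-arm summaries as description. No new data are needed. The cost is a little more analysis, chiefly the caregiver model, a few extra table rows, and an interval that will look wide. That width is a fair picture of what 20 v 20 can show.

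Suggested text: *For Hyp 1c we will also estimate the between-arm difference (DECIDES + coach minus DECIDES) in SUS score, adjusted for age stratum and separately for AYA and caregivers, and in participation proportion, each with a 95% CI. These estimates are exploratory and no test will be made.*

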6.2 Secondary Endpoints

The secondary objective is to evaluate preliminary efficacy of DECIDES using a randomized trial.

Hyp 2a and Hyp 2b. Because all measures are continuous, the primary analyses will be summarizing mean and 95% CI by groups and two-sample t test comparing groups for the post-intervention outcome measures. With the sample size of 20 family units for each DECIDES group and 10 family units for usual care, we will have 80% power to detect an effect size of 1.26 (that is, mean difference between the two groups is 1.26 x Standard Deviation).

Hyp 2c. Each AYA and caregiver will have two value scores: Σ factors endorsed as supporting enrollment/ Σ factors endorsed as not supporting enrollment. Consistency of value to enrollment decision will be evaluated with Tetrachoric correlation with 95% CI.

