1.1.2 AYA Cancer Clinical Trial Decision-Making

We evaluated AYA with cancer, primary caregiver, and oncology provider Phase III clinical trial decision-making experiences.⁽¹⁾ From content analysis, AYA perceived that they had no role (38.4%) or a minor role (30.8%) in the clinical trial enrollment decision; they conveyed a sense of resignation because they viewed themselves as relying on their parents to make treatment decisions at diagnosis. Caregivers and providers felt challenged to include AYA in the treatment decision-making process at diagnosis, and providers noted uncertainty in how

to provide balanced information about treatment options and minimize coercion. AYA and caregivers who refused a Phase III clinical trial cited prolonged treatment with limited benefit, but many AYA and caregivers did not accurately remember whether the cancer treatment had been standard of care or on a clinical trial.

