2.2 Secondary Objectives (or Aim)

The secondary objective is to evaluate preliminary efficacy of DECIDES using a randomized trial.

Hyp 2a. AYA randomized to DECIDES and DECIDES + coach will report greater involvement in and shared decision-making than AYA assigned to Usual Care.

Hyp 2b. AYA and caregiver(s) randomized to DECIDES and DECIDES + coach will report more positive decision-making processes (greater knowledge of their cancer and clinical trials, more balanced attitudes toward clinical trials, and more decision certainty, satisfaction and self-efficacy) compared with those assigned to Usual Care.

Hyp 2c. For DECIDES and DECIDES + coach participants who are offered enrollment on a clinical trial, the enrollment decision (yes/no) will align with AYA values.

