5.2 Self-Report Measures

Demographics: Variables will be collected based on AYA and caregiver(s) self-report and review of the patients' electronic health record. Demographic variables include age, gender, race/ethnicity, education/work, health care, and family history.

Intensity of Treatment Rating Scale (ITR-3): The revised version of a reliable and valid method for classifying pediatric oncology treatment protocols. This scale, completed by a medical provider, categorizes the intensity of pediatric cancer treatment from least through most intensive based on treatment modality and stage/risk level for the patient. ⁽⁹⁹⁾

Acceptability of the Decision Aid: A study-team developed measure used to obtain acceptability ratings from AYA and caregiver(s) (assigned to DECIDES or DECIDES + coach only). This measure is based on The Ottawa Hospital's measure of acceptability ratings regarding comprehensibility of components of a decision aid, its length, pace, amount of information, balance in presentation of information about options, and overall suitability for decision making. ⁽⁶⁾

Systems Usability Scale (SUS): This is a cost-effective, 10-item scale that is widely used to obtain a reference score for participants' view of a product's usability. This scale includes 10 statements that are scored on a 5-point scale of strength of agreement. Final scores can range from 0 to 100, in which higher scores indicate better usability. AYA and caregiver(s) (assigned to DECIDES or DECIDES + coach only) and oncology health care providers will complete this scale. ^(36,71)

Control Preferences: This scale assesses patient decision-making preferences and roles (i.e., patient's preferred role [baseline] versus the role they actually played in making a treatment decision [post-intervention]). This scale has been adapted for use in this study to assess caregiver decision-making preferences and roles, as well (i.e., caregiver's preferred role of patient [baseline] versus the role the patient actually played in making a treatment decision [post-intervention]). Decision-making preferences and roles are evaluated using three categories: 1) patient led, 2) shared, or 3) oncologist/caregiver led. ^(74,75)

Physician Decision Making Scale: A 5-item scale that measures physician involvement in medical decision-making. Items are rated on a 3-point scale ranging from 1 ("Yes, definitely") to 3 ("No"). Higher scores reflect lower involvement in decision-making. ⁽¹⁰⁰⁾

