Shared Decision-Making Questionnaire (SDM-Q-9): This is a brief, valid, and reliable 9-item questionnaire that measures the degree to which patients are involved in the process of decision-making (for preference-sensitive decisions, in which there are several treatment options for a particular disease) from the perspective of the patient. The SDM-Q-Doc (Physician Version) has been adapted for use in this study to measure the degree to which patients are involved in the process of decision-making from the perspective of the caregiver. Items are scored on a 6-point scale ranging from "completely disagree" (0) to "completely agree" (5), and a total sum score is calculated (ranging in values between 0-45). ⁽⁹⁴⁾

Adolescent and Young Adult Health Outcomes and Patient Experiences (AYA HOPE) Survey: Information needs are assessed using thirteen items from the AYA HOPE study survey. Participants indicate if they need more information on a range of topics related to cancer medical care and support services. The response options ("I need some more information" and "I need much more information" are collapsed and categorized as "unmet information need"; while the response options "I have enough information" and "Does not

apply" are collapsed and categorized as "met information need". Unmet information need (count) is categorized as low (0-3), intermediate (4-8), or high (9-13).^(76,77)

Knowledge of Clinical Trials: This is a 25-item true/false rating assessment used to assess participant understanding of clinical trials and informed consent processes.⁽⁶⁴⁾

Pediatric Research Participation Questionnaire (PRPQ): The PRPQ is a 12-item questionnaire for AYA (age 15-29) and caregivers (of AYA) about participation in a clinical trial. Items are rated on a 5-point scale, ranging from "not at all" (1) to "extremely" (5).^(15,16)

Decisional Conflict Scale: This is a valid and reliable 16-item scale, delivered in statement format (Version A), that measures personal perceptions of: uncertainty in choosing options; modifiable factors contributing to uncertainty (i.e., feeling uninformed, unclear about personal values, and supported in decision making); and effective decision making (i.e., feeling the choice is informed, values-based, likely to be implemented, and expressing satisfaction with the choice). Items are rated on a 5-point scale ranging from "strongly agree" (0) to "strongly disagree" (4). Higher scores indicate higher decisional conflict.

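### Section 6.2 plans means and t tests on the ground that every measure is continuous, but Control Preferences, one of the three Hyp 2a measures, has three categories with shared in the middle, so a mean code cannot show whether more decisions were shared.

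*Combined protocol and SAP*

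**What the plan says.** Section 6.2 covers Hyp 2a and Hyp 2b together: "Because all measures are continuous, the primary analyses will be summarizing mean and 95% CI by groups and two-sample t test comparing groups". The comparison is of outcomes at T2, after the intervention. The section adds that 20 families per DECIDES arm and 10 in Usual Care give 80% power for a difference of 1.26 SD.

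Hyp 2a (section 2.2) reads: "AYA randomized to DECIDES and DECIDES + coach will report greater involvement in and shared decision-making than AYA assigned to Usual Care". The matching construct in Table 1 is "AYA Involvement in Shared Decision-Making", with three measures, all at T2: Control Preferences, the Physician Decision-Making Scale and SDM-Q-9.

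Section 5.2 describes Control Preferences thus: "Decision-making preferences and roles are evaluated using three categories: 1) patient led, 2) shared, or 3) oncologist/caregiver led". By contrast, SDM-Q-9 is a score: "a total sum score is calculated (ranging in values between 0-45". The Physician Decision Making Scale has five items, each rated 1 to 3.

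Neither section 6 nor section 5.2 gives Control Preferences a scoring rule, a dichotomy or a categorical analysis. The only other statement is the opening line of section 6, that all measurements will be summarized.

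**The concern.** The reason given for the t test is untrue of one named outcome. The only way to apply section 6.2 to Control Preferences is to average its category codes. Averaging ordered codes is sometimes a tolerable shortcut, but here the category that Hyp 2a names, shared, lies in the middle. Movement into a middle category is not identified by a mean.

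Hyp 2a predicts both more involvement and more shared decision-making. A lower mean code could come from other-led decisions becoming shared, or from fewer of them becoming patient led. A significant t test could then be reported as support for shared decision-making when the proportion of shared decisions had not changed. And because no category split is named in advance, one could be chosen after the data are seen.

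**Working it through.** **The plan's own figure.** Inputs from section 6.2: n = 10 v 20, difference 1.26 SD, power 80%. Alpha is not stated. Noncentral t with 28 degrees of freedom gives 88.1% power at two-sided 0.05 (80% power is reached at 1.124 SD) and 80.6% at two-sided 0.025 (1.251 SD). The stated figure therefore fits an alpha near 0.025; the plan should state its alpha. Nothing below depends on this, but the figure describes a mean difference on a score, not a difference in category proportions.

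**What the mean measures.** Let p1, p2, p3 be the proportions patient led, shared and other led, coded 1, 2, 3. Since p1 + p2 + p3 = 1,

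mean = p1 + 2·p2 + 3·p3 = 2 + (p3 − p1),

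variance = (p1 + p3) − (p3 − p1)².

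The mean depends only on the gap between the two outer categories.

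**Assumed proportions.** The documents give none for this scale. A mostly other-led Usual Care arm is suggested by section 1.1.2: "AYA perceived that they had no role (38.4%) or a minor role (30.8%) in the clinical trial enrollment decision", together 38.4 + 30.8 = 69.2%. I take 10/20/70 as the main Usual Care case.

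- 10/20/70: mean 2 + 0.70 − 0.10 = 2.6; variance 0.80 − 0.36 = 0.44.
- 10/80/10: mean 2 + 0.10 − 0.10 = 2.0; variance 0.20.
- 40/20/40: mean 2 + 0.40 − 0.40 = 2.0; variance 0.80.

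Standardized differences, with the SD pooled 9:19:

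- 10/20/70 v 10/80/10: 0.6 / √[(9×0.44 + 19×0.20)/28] = 0.6/0.526 = 1.14.
- 10/20/70 v 40/20/40: 0.6 / √[(9×0.44 + 19×0.80)/28] = 0.6/0.827 = 0.73.

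**Rejection rates.** These come from exact enumeration of all multinomial outcomes (66 for n = 10, 231 for n = 20) at two-sided 0.05. Section 6.2 does not say pooled or Welch, so both are shown.

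| Usual Care v one DECIDES arm | Change in shared (points) | Means | Pooled t | Welch t | Fisher, shared | Fisher, patient led or shared |
|---|---|---|---|---|---|---|
| 10/20/70 v 10/80/10 | +60 | 2.6 v 2.0 | 74.8% | 62.6% | 87.5% | 92.3% |
| 10/20/70 v 40/20/40 | 0 | 2.6 v 2.0 | 43.2% | 50.9% | 2.2% | 23.6% |
| 10/20/70 v 20/60/20 | +40 | 2.6 v 2.0 | 63.9% | 59.2% | 44.5% | 72.7% |
| 10/20/70 v 30/50/20 | +30 | 2.6 v 1.9 | 70.6% | 67.9% | 27.3% | 72.7% |
| 40/20/40 v 10/80/10 | +60 | 2.0 v 2.0 | 11.8% | 5.6% | 87.5% | 42.1% |

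The first three rows have the same means and different changes in shared decisions. The last row is less typical, because its Usual Care arm is not mostly other-led; it shows that a 60-point rise drawn equally from both outer categories leaves the mean unchanged.

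**Precision of the alternative.** For 16/20 v 2/10 shared, the difference is 80% − 20% = 60 points, with a Newcombe 95% CI of 22 to 79 points.

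**The case against.** The strongest reply has four parts.

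1. *The plan never says that codes will be averaged.* The numbers in section 5.2 may be list labels, and counts are not excluded. That is true, but section 6.2 speaks of all measures and names means and t tests. If something else is intended for this outcome, it has to be written down.

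2. *Table 1 has a single construct.* If it means only more AYA involvement, the categories are ordered and the mean moves the right way. That reading is possible, and the t test is not always blind: it does respond when other-led decisions become shared. But Hyp 2a names shared decision-making as well as involvement, and the mean cannot separate the two. SDM-Q-9 does cover the construct with a proper score, which limits the damage without making the Control Preferences result interpretable.

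3. *The t test holds its size.* With both arms at 10/20/70, enumeration gives 5.0% (pooled) and 6.0% (Welch). This stands. The fault is in what a rejection means, not in false positives under no difference.

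4. *Proportions can cost power.* This stands too. For 10/20/70 v 20/60/20, Fisher on shared has 44.5% against 63.9% for the pooled t. For 10/20/70 v 40/20/40, Fisher on patient led or shared has 23.6% against 43.2%, although involvement truly rises from 30% to 60%. For a moderate shift, 10/20/70 v 20/40/40, the figures are 29% (pooled t), 13% (shared) and 24% (patient led or shared). The case for the change is interpretability, not power.

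**Conclusion.** The concern holds. Sections 6.2 and 5.2 contradict each other directly, and the identity for the mean shows, without any assumed rates, that a mean code carries no separate information on the proportion shared. The size of the practical effect does rest on assumed category proportions, on one DECIDES arm of 20 against 10 in Usual Care, and on two-sided 0.05. Under those assumptions, identical means of 2.6 v 2.0 arise with a 60-point rise in shared decisions or with none, and the pooled t test rejects in 75% and 43% of trials.

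The reach is limited to one of three measures for one secondary hypothesis. SDM-Q-9 and the Physician Decision Making Scale are unaffected, as are the primary acceptability and feasibility analyses. It should be fixed before analysis, but it does not threaten the trial.

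**What to change.** In section 6.2:

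- Delete the claim that all measures are continuous. Limit means, t tests and the 1.26 SD power statement to the summed or scored scales.
- Report T2 Control Preferences as counts and percentages in all three categories, by group.
- Prespecify two AYA-reported proportions for Hyp 2a: patient led or shared (involvement), and shared (shared decision-making). For each, give the difference between each DECIDES arm and Usual Care with an exact or score-type 95% CI and Fisher's exact test. Say how the two are read if they disagree.
- Summarize the caregiver version the same way.
- State the limits: intervals will be wide at 20 v 10, and either proportion can have less power than a test on the ordered codes.

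At the same time, reconcile section 5.2, which has the preferred role collected at baseline, with Table 1, which shows Control Preferences at T2 only.

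The cost is a few sentences in the plan and a few lines of analysis code, with no new data or participants. The price is the wider intervals and the possible loss of power shown above.

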3.1.3 Assessment Time Points

All AYA and caregiver(s) that enroll to participate in the study will complete an electronic baseline assessment at time of enrollment (prior to randomization) and again at post-intervention (i.e., approximately six-weeks after date of randomization). Additionally, AYA and caregiver(s) randomized to DECIDES or DECIDES + coach will also complete an audio or video-recorded semi-structured qualitative interview with a member of the study team via Microsoft Teams after the post-intervention assessment.

Oncology health care providers of enrolled AYA and caregiver(s) will be invited to preview the DECIDES website, participate in an electronic rating scale and complete an audio-recorded semi-structured qualitative interview with a member of the study team via Microsoft Teams.

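### Section 6.2 compares arms with an unadjusted t test on post-intervention scores, leaving the pre-randomization score (two Hyp 2b outcomes) and the age stratum unused: valid, but avoidably inefficient

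*Combined protocol and SAP*

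**What the plan says.** Section 6.2 (Secondary Endpoints) covers Hyp 2a and 2b in one sentence: "the primary analyses will be summarizing mean and 95% CI by groups and two-sample t test comparing groups for the post-intervention outcome measures". It gives 80% power at 1.26 SD for 20 families in each DECIDES arm and 10 in Usual Care. It states no alpha, and the protocol specifies no adjusted analysis anywhere else.

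Other sections supply what an adjusted analysis would need:

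- **Timing.** Under section 3.1.3, participants "complete an electronic baseline assessment at time of enrollment (prior to randomization) and again at post-intervention". T1 scores therefore cannot be affected by allocation.
- **Outcomes.** Hyp 2b (section 2.2) expects "greater knowledge of their cancer and clinical trials, more balanced attitudes toward clinical trials". In Table 1 (section 5.3), Knowledge of Clinical Trials and the PRPQ, the latter under "Attitudes to Clinical Trials", are listed at both T1 and T2 for AYA and caregivers.
- **Stratification.** Section 8.1.1: "The randomization will be stratified by two age categories, under 18 years old and 18 years or older". It continues: "For each stratum, we use a blocked randomization of block size of 5". Half of the patients are expected in each stratum.
- **Covariates.** Table 1 stars six constructs (eight instruments) as covariates. Section 6.2 gives them no role.

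**The concern.** When an outcome has a score from before randomization, a comparison of post-intervention scores alone leaves in the error term all the variation that the earlier score would explain. The same applies to a stratification factor that predicts outcome. In addition, if stratification succeeds in balancing a prognostic factor, an analysis that ignores it overstates the standard error, and the test becomes conservative.

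Preliminary efficacy is what is at stake. With 10 Usual Care families only very large differences are detectable, so precision that can be had from data already collected should not be given up. Acceptability and feasibility, the primary objective, are untouched. The randomized comparison is not biased.

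The starred covariates raise a related, smaller point. Measures labelled as covariates but given no place in the analysis leave open until after the data are seen which of them, if any, will be used.

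**Working it through.** **Inputs.** From the documents: 20 versus 10 families per comparison, 80% power, effect in SD units, two age strata, blocks of 5 at 1:2:2. Assumed: two-sided alpha of 5% or 2.5%, T1-T2 correlation r from 0 to 0.7, one score per family.

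**1. The plan's own figure.** For an effect d, the noncentrality of the t test is d / √(1/20 + 1/10) = d / 0.387, with 30 − 2 = 28 degrees of freedom. At d = 1.26 this is 3.25. Power is 88.1% at two-sided 5% and 80.6% at two-sided 2.5%. The stated 80% is therefore approximately reproduced at two-sided 2.5%; that this is the intended alpha is an inference. The effects detectable with 80% power are 1.124 SD (5%) and 1.251 SD (2.5%).

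**2. Adding T1 score and age stratum.** Error degrees of freedom fall from 28 to 26. The variance of the arm difference is multiplied by (1 − r²)(1 + 1/26), the second factor allowing for chance imbalance in the T1 score. At r = 0.5, for example, this is 0.75 × 1.0385 = 0.779. The stratum is assumed to explain nothing.

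| Analysis | Detectable SD, 5% | Detectable SD, 2.5% | Power at 1.0 SD, 5% |
|---|---|---|---|
| t test | 1.124 | 1.251 | 70% |
| ANCOVA, r = 0 | 1.149 | 1.279 | 68% |
| ANCOVA, r = 0.2 | 1.126 | 1.254 | 70% |
| ANCOVA, r = 0.3 | 1.096 | 1.221 | 72% |
| ANCOVA, r = 0.5 | 0.995 | 1.108 | 80% |
| ANCOVA, r = 0.7 | 0.820 | 0.914 | 93% |

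Break-even is r = 0.21 at either alpha. Simulation agrees: at a true difference of 1.124 SD and two-sided 5%, t test versus ANCOVA power is 80% versus 78% (r = 0), 80% versus 82% (0.3), 81% versus 89% (0.5) and 80% versus 97% (0.7).

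**3. Age stratum only, for outcomes without a usable T1 score.** With 27 degrees of freedom and two-sided 5%, the detectable effect is 1.126, 1.097 or 1.068 SD if age explains 0, 5 or 10% of variance. Against 1.124 SD that is a gain of about 0 to 5%.

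**4. Type I error of the unadjusted test.** With 25 families per stratum, 1:2:2 allocation gives 25 × 1/5 = 5 Usual Care and 25 × 2/5 = 10 in each DECIDES arm. Loss between the 65 who may be enrolled and the 50 evaluable can disturb this, so three layouts were simulated at nominal 5% (families under 18 / 18 or over):

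| Usual Care vs DECIDES arm | Age explains 10% | Age explains 20% |
|---|---|---|
| 5/5 vs 10/10 | 3.9% | 2.8% |
| 4/6 vs 11/9 | 4.6% | 4.0% |
| 3/7 vs 10/10 | 5.1% | 5.0% |

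The stratum-adjusted model stays at 4.9 to 5.1% throughout.

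**5. Entering every starred measure.** Eight covariates plus the stratum leave 30 − 2 − 9 = 19 degrees of freedom. If they explain nothing, the detectable effect rises to 1.38 SD. The loss is recovered only if they jointly explain about a third of the variance.

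**The case against.** The strongest case against is that the planned test is valid, the aim is preliminary, and the benefit depends on a correlation that the documents do not give. Below r of about 0.2 there is no gain, and at r = 0.3 it is about 2%. Even at r = 0.7 only differences above 0.8 SD are detectable. For outcomes adjusted for age alone the gain is close to nil. All of this stands. It makes the point a recommended improvement and not the correction of an error. The trade still favours adjustment: the worst case is 1.12 to 1.15 SD, against 1.12 to 0.99 SD at r = 0.5. T1 and T2 use the same instrument in the same people roughly two months apart or less, so r above 0.2 is plausible, though undocumented.

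A second objection is technical. With 2:1 allocation, a common-slope ANCOVA can be anti-conservative if the T1-T2 slope differs between arms. With assumed slopes of 0.6 in DECIDES and 0.2 in Usual Care, simulated type I error is 6.7 to 6.9% at nominal 5%; with the slopes reversed it is about 4%. This stands as a caveat. An HC3 robust variance brings the 0.6/0.2 case to 4.4%.

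Third, the PRPQ has a four-factor structure (section 1.1.1), and no single outcome score is defined in section 5.2. True, but the planned t test needs the same choice, and adjustment applies to whichever score is named.

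Finally, the figures assume one score per family. AYA aged 18 or over may join alone and some families supply two caregivers, so caregiver comparisons will have other numbers. That changes the sizes, not the direction.

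**Conclusion.** The concern holds. The planned analysis is valid but uses neither a pre-randomization score available for two Hyp 2b outcomes nor the factor on which allocation is stratified. For Knowledge of Clinical Trials and the PRPQ the cost is a detectable difference of 1.12 SD where 0.99 SD (r = 0.5) or 0.82 SD (r = 0.7) could be had at two-sided 5%. If r is below about 0.2, adjustment gains nothing and loses at most 0.03 SD. For the remaining continuous outcomes the gain is 0 to 5% if age explains up to 10% of variance.

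These sizes rest on assumed alpha and r, one score per family, 20 versus 10 evaluable families and, for the ANCOVA figures, a common slope across arms. Only the secondary objective is affected. The change is advisable; the validity of the trial does not depend on it.

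**What to change.** For each pairwise comparison now planned as a t test, revise section 6.2 as follows.

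1. **Knowledge of Clinical Trials and PRPQ:** ANCOVA of the T2 score on arm, T1 score and age stratum (under 18 / 18 or over). Name the PRPQ score to be analysed.
2. **Other continuous outcomes:** linear model of the T2 score on arm and age stratum, adding the T1 score only where one is collected. The T1/T2 columns for the decision scales cannot be read with certainty in the extracted Table 1.
3. **Reporting:** give the adjusted difference with 95% CI and keep unadjusted means and CIs as description. Include an HC3 robust standard error as protection against unequal slopes.
4. **Starred covariates:** state their role. With 30 families per comparison, do not enter them all; any that are used should be few, prespecified and taken from T1.

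Control Preferences is outside this change. Section 5.2 says "Decision-making preferences and roles are evaluated using three categories", and its baseline item asks about preferred role, not the role played.

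The cost is plan wording and one error degree of freedom (28 to 27) for the stratum, or two (28 to 26) with the T1 score. If r proves to be below about 0.2, there is also a small loss of precision for the two outcomes in item 1.
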